### 9.3 Adverse Events

Adverse events (AEs) will be documented on the AE eCRF and monitored continuously throughout the study. Adverse events will be coded using the Medical Dictionary for Regulatory Activities (MedDRA), latest version, associating lower-level terms with PT and SOC by the primary hierarchy.

Treatment Emergent Adverse Events (TEAEs) are those events with onset date occurring during the on-treatment period. The tables will display counts and percentages of patients who reported at least one TEAE in each SOC represented in the AE data. Within each SOC, the tables will display the counts and percentages of patients reporting at least one TEAE, as designated by the PT.

The severity of adverse events will be graded using the NCI Common Toxicity Criteria for Adverse Events (CTCAE version 5.0). The intensity is assigned a grade of 1 through 5 using the following CTCAE guidelines: Grade 1 – Mild; Grade 2 – Moderate; Grade 3 – Severe; Grade 4 – Life-threatening; Grade 5 – Death.

The causality of AE are reported as either related to study drug or not related to study drug for each study drug. Related AEs are those related to any study drug (i.e., at least one of the study drugs).

Pfizer Inc. / Protocol: TTI-621-03/C4961003  
IQVIA Biotech (Confidential) Project # YXA42460

If a patient has multiple occurrences of an adverse event, the strongest level of relationship to study drug(s) and the worst toxicity grade a patient experiences for a given AE will be used in these tables. No imputation will be performed for missing toxicity grade or causality data.

AEs that have missing onset dates will be considered as TEAE unless the stop date is known to be prior to the first administration of the study medication. If the AE onset date is partial, the date will be correlated as far as possible with the date of first dose of study medication. AE will be assumed to be TEAE, unless there is clear evidence (through comparison of partial dates) to suggest that the adverse event started prior to the first dose of study medication. Detailed imputation rules can be found in section 6.3. If patients died during the study and experienced AEs at the time of death, the AEs that lead to death will use death date as the AE end date; otherwise, AEs that do not lead to death will be reported as ongoing.

Adverse Events of Special Interest (AESI) include the following:

- Thrombocytopenia: Haematopoietic thrombocytopenia – SMQ Broad
- Anemia: Haematopoietic erythropenia – SMQ broad
- Hemorrhage: Haemorrhage terms (excl. laboratory terms) – SMQ narrow
- Infusion related reactions (PT of Infusion-related reaction as recorded on the Adverse Event CRF)

The following TEAE summary tables will be produced by treatment group as described in Section 6.1:

- a. An overall summary of safety will summarize the numbers (and percentages) of patients with the following:
  - TEAEs (separately for combination period and monotherapy period, and overall), where combination period is defined as from the date of first study treatment to the date of last doxorubicin + 21 days
  - Grade  $\geq 3$  TEAEs (separately for combination period and monotherapy period, and overall)
  - Treatment-related TEAEs (separately for combination period and monotherapy period, and overall)
  - Treatment-related grade  $\geq 3$  TEAEs (separately for combination period and monotherapy period, and overall)
  - Serious TEAEs
  - Treatment-related Serious TEAEs
  - TEAEs leading to dose reduction (of PF-07901800 and doxorubicin, separately)
  - TEAEs leading to drug interruption (of PF-07901800 and doxorubicin, separately)

Pfizer Inc. / Protocol: TTI-621-03/C4961003  
IQVIA Biotech (Confidential) Project # YXA42460

- TEAEs leading to permanently discontinued study drug (PF-07901800, doxorubicin, and both)
- Treatment related TEAEs leading to permanent discontinuation of PF-07901800
- Treatment-related TEAEs leading to permanent discontinuation of doxorubicin
- Treatment-related TEAEs leading to permanent discontinuation of both drugs
- TEAEs leading to death
- Treatment-related TEAEs leading to death
- At least one TEAE of special interest: Thrombocytopenia SMQ (broad)
- At least one TEAE of special interest: Anemia SMQ (broad)
- At least one TEAE of special interest: Hemorrhage SMQ (narrow)
- At least one TEAE of special interest: Infusion related reactions

b. Separate summaries of TEAEs by SOC and PT, as follows:

- TEAEs by maximum severity (separately for combination period and monotherapy period, and overall)
- Treatment-related TEAEs (separately for combination period and monotherapy period, and overall)
- DLT
- Serious TEAEs
- Treatment-related Serious TEAEs
- TEAEs leading to dose reduction (of PF-07901800 and doxorubicin separately)
- TEAEs leading to drug interruptions (of PF-07901800 and doxorubicin separately)
- TEAEs leading to permanent discontinuation (of PF-07901800 and doxorubicin separately, and both)
- Treatment-related TEAEs leading to permanent discontinuation of (of PF-07901800 and doxorubicin separately, and both)
- TEAEs leading to death
- Treatment-related TEAEs leading to death

c. Separate summaries of TEAEs by PT, as follows:

- Most common TEAEs (Any grade and Grade  $\geq$  3)  
Most common Treatment-related TEAEs (Any grade and Grade  $\geq$  3)

d. Summary of TEAEs (any grade and Grade  $\geq$  3) of special interest will be summarized by SMQ and PT, as applicable:

- Thrombocytopenia (broad)
- Anemia (broad)

Pfizer Inc. / Protocol: TTI-621-03/C4961003

IQVIA Biotech (Confidential) Project # YXA42460

- Hemorrhage (narrow)
- e. Summary of infusion related reactions (any grade and Grade  $\geq 3$ ) by SOC and PT

The following AE listings will be produced, sorted by dose cohort, patient, and timing, with relevant information:

- All AEs
- All DLTs
- AEs leading to death
- COVID-19 related AEs

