**13.1. Definition of Adverse Events****13.1.1. Adverse Event**

An adverse event is any untoward medical occurrence or the worsening of a pre-existing medical condition following or during exposure to a pharmaceutical product, whether or not considered causally related to the product. Development of new disease lesions or disease progression is not considered an adverse event.

All AEs and SAEs occurring in a patient during the active collection period as described in [Section 13.5.3](#). will be recorded on the appropriate CRF from the signature of the informed consent. All SAEs must be reported on the CT SAE Report Form to Pfizer Safety immediately upon awareness and under no circumstance should this exceed 24 hours. A worsening of a condition/disease recorded in the medical history is reportable as an AE. Documentation must be supported by an entry in the patient's source medical records. Laboratory abnormalities requiring treatment or considered by the investigator to be clinically relevant should be reported in the CRF as an AE. Each AE is to be evaluated for duration, severity and causal relationship with the IP.

For the purposes of this study, events that are unequivocally due to disease progression should not be reported as AEs unless the outcome is fatal within the active collection period. Hospitalization due to signs and symptoms of disease progression should not be reported as an SAE. If the malignancy has a fatal outcome during the study, the event leading to death must be recorded as an AE on the CRF, and as an SAE with CTCAE Grade 5 if it occurs during the active collection period. Symptoms of the disease under study/lack of efficacy should not be classified as AEs as long as they are within normal day-to-day fluctuations or expected progression of the disease.

The development of a new cancer should be regarded as an AE and will generally meet at least one of the SAE criteria. New cancers are those that are not the primary reason for study treatment and have been identified after the patient's inclusion in this study. They do not include metastases of the original cancer.

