#### 13.5.3. Time Period and Frequency for Collecting AE and SAE Information

The time period for actively eliciting and collecting AEs and SAEs (“active collection period”) for each patient begins from the time the patient provides informed-consent, which is obtained before undergoing any study-related procedure and/or receiving study intervention, through and including a minimum of 30 calendar days after the last administration of the study intervention.

For patients who are screen failures, the active collection period ends when screen failure status is determined.

If the patient withdraws from the study and also withdraws consent for the collection of future information, the active collection period ends when consent is withdrawn.

If a patient permanently discontinues or temporarily discontinues study intervention because of an AE or SAE, the AE or SAE must be recorded on the CRF and the SAE reported using the CT SAE Report Form.

Investigators are not obligated to actively seek information on AEs or SAEs after the patient has concluded study participation. However, if the investigator learns of any SAE, including a death, at any time after a patient has completed the study, and they consider the event to be reasonably related to

the study intervention, the investigator must promptly report the SAE to Pfizer using the CT SAE Report Form.

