#### **13.5.4. Documentation**

All AEs (serious and non-serious) occurring within the period of observation for the study must be documented in the CRF with the following information, where appropriate. (The period of observation for the study is described in [Section 13.5.3](#)).

- AE name or term
- When the AE first occurred (start date)
- When the AE stopped (stop date or an indication of “ongoing”)
- Severity of the AE
- Seriousness (hospitalization, death, etc.)
- Actions taken
- Outcome
- Investigator opinion regarding the AE relationship to the IP(s)

All nonserious AEs and SAEs occurring in a patient during the active collection period which begins after obtaining informed consent as described in [Section 13.5.3](#), will be recorded on the AE section of the CRF.

The investigator or designee is to record on the CRF all directly observed and all spontaneously reported AEs and SAEs reported by the patient.

The investigator must record his or her reasoning for this decision in the patient’s medical record and as a comment on the CRF

Reporting of AEs and SAEs for patients who fail screening are subject to the CRF requirements as described in [Section 13.5.3](#).

As part of ongoing safety reviews conducted by the sponsor, any nonserious AE that is determined by the sponsor to be serious will be reported by the sponsor as an SAE. To assist in the determination of case seriousness, further information may be requested from the investigator to provide clarity and understanding of the event in the context of the clinical study.

If a patient begins a new anti-cancer therapy, the recording period for nonserious AEs ends at the time the new treatment is started; however, SAEs must continue to be recorded on the CRF during the above indicated active collection period. Note that a switch to a commercially available version of the study intervention is considered as a new anti-cancer therapy for the purposes of SAE reporting.

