## 6.4 Definition of on-treatment period

Safety endpoints will be summarized based on the on-treatment period, unless otherwise specified.

On-treatment period is defined as the time from the first dose of study treatment through minimum (30 days + last dose of study treatment, start day of new anti-cancer therapy captured on the “Survival Status” CRF).

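### SAP 9.3 defines a TEAE by onset date alone, so an AE logged in screening that worsens on treatment can drop out of the TEAE tables if it is kept as one record

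*SAP*

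**What the plan says.** SAP 9.3 gives the definition: "Treatment Emergent Adverse Events (TEAEs) are those events with onset date occurring during the on-treatment period". The period comes from SAP 6.4: "On-treatment period is defined as the time from the first dose of study treatment through minimum" of two dates, namely 30 days after the last dose and the start of new anti-cancer therapy. Screening therefore lies outside it. The summary tables listed in SAP 9.3 a–e are all TEAE tables: the overall summary, those by SOC and PT, maximum severity, serious, related, dose actions, death and AESI.

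The protocol collects AEs from earlier. Under Protocol 13.5.3 active collection "begins from the time the patient provides informed-consent", and Protocol 13.5.4 takes the start date of a record to be the date of first occurrence. Protocol 13.1.1 includes in the meaning of an AE "the worsening of a pre-existing medical condition following or during exposure to a pharmaceutical product". It adds: "A worsening of a condition/disease recorded in the medical history is reportable as an AE". It has no matching sentence for an event that is already on the AE log when it worsens.

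**The concern.** Screening runs from Day -28 to Day -1, so AE records with a start date before the first dose will exist. Protocol 2 (Synopsis) expects some patients to enter with Grade 1 or Grade 2 symptoms or laboratory values. If such an event is on the AE log and becomes Grade 3 or serious after dosing, a rule that looks only at the start date classes it as not treatment-emergent. Yet the worsening happened on treatment and is what the protocol calls an AE.

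At stake is a wrong count in the safety tables rather than missing detail. The same clinical course could be counted or not depending on which form the site used in screening and how it recorded the change. Safety is a primary objective in both parts of the study, and the expansion cohorts are small enough for one patient to be visible in a single-term row.

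**Working it through.** The plan states no figure on this point, so the check is a reading of the rules side by side, followed by the arithmetic for one patient.

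**Step 1. Inputs**
- AE collection starts at consent (Protocol 13.5.3).
- Screening is Day -28 to -1 (Protocol Table 24, SAP 4.5).
- The start date is the date of first occurrence (Protocol 13.5.4).
- The on-treatment period starts at the first dose (SAP 6.4).
- A TEAE needs its onset date in that period (SAP 9.3).
- The rules for missing and partial dates (SAP 6.5, SAP 9.3) also ask only when the event began. None mentions worsening.

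**Step 2. One clinical course, recorded in different ways.** Take a Grade 1 finding on Day -10 that reaches Grade 3 on Cycle 1 Day 8.

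| Recorded in screening as | Recorded at worsening as | Start date used | TEAE under SAP 9.3? |
|---|---|---|---|
| AE, complete date | same record, grade updated | Day -10 | No |
| AE, complete date | new AE record | Cycle 1 Day 8 | Yes, Grade 3 |
| Medical history | AE (reportable under Protocol 13.1.1), dated at worsening | Cycle 1 Day 8 | Yes, Grade 3 |
| Laboratory value not logged as an AE | AE, dated at worsening | Cycle 1 Day 8 | Yes, Grade 3 |
| AE, day missing, in the month and year of first dose | same record | imputed to first dose | Yes |

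Only the first row is lost, and the documents do not say whether it or the second row is what sites do. The last row shows an odd effect: an incompletely dated screening event is counted where a fully dated one is not.

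**Step 3. What remains visible in the first row**
- The event stays in the All AEs listing (SAP 9.3).
- A gradable hematology or chemistry result also appears in the shift from baseline grade to worst on-treatment grade (SAP 9.5).
- Dose reductions, interruptions and omissions are summarized from the drug administration forms (SAP 9.1).
- Discontinuation reasons appear in SAP 7.2 and deaths in SAP 9.4.
- Pain, fatigue and other non-laboratory events have no shift table.

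**Step 4. Size of one lost patient.** The change in a row percentage is 1/n. SAP 4.3.2 gives cohort sizes of 31 (planned), 18 and 13:
- 1/31 = 3.2 points
- 1/18 = 5.6 points
- 1/13 = 7.7 points

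The tables count patients with at least one event, so these are upper limits. A row changes only if the patient has no other qualifying event in it. In broad rows that will often not be so: in TTI-621-01, 223 of 235 patients (95%) had at least one TEAE (Protocol 3.5.2.1.2). The effect falls mainly on single preferred-term rows.

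**The case against.** The strongest reply is that the exclusion is conditional. Protocol 13.1.1 makes the worsening itself an AE, so its date of first occurrence can be read as the date of worsening, which falls on treatment. Form-completion instructions, which are not part of these documents, may require a new record. The SAP sentence that "the worst toxicity grade a patient experiences for a given AE will be used in these tables" does not settle the matter, because it is about a patient with several occurrences of an event and says nothing on keeping one record. This objection stands in part: the loss is possible, not certain. It does not remove the gap, because the protocol states the rule for medical-history conditions and is silent on events already on the AE log.

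The affected group is also narrow. The event must arise between consent and first dose, be logged as an AE, persist, and then worsen. From the entry limits for hemoglobin (9 g/dL) and platelets (100 × 10⁹/L), a reader might infer that mild cytopenias at entry are routinely lost from the anemia and thrombocytopenia rows. The documents do not support that. Under Protocol 13.6 a laboratory abnormality not reported within a clinical syndrome is an AE only if it leads to an intervention, is a DLT or is judged clinically relevant. A mild screening value would usually not be logged, and its later worsening would carry an on-treatment onset. An infusion-related reaction to study drug cannot precede the first infusion.

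A reader might also put a rate on affected patients, or take 3.2 points off a row for each one. The documents give no rate, and Step 4 shows why the points are only an upper limit.

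**Conclusion.** The point holds in a limited form. SAP 9.3 has no clause for worsening. An AE logged before first dose that increases in grade or becomes serious on treatment is left out of the tables in 9.3 a–e if it is kept as one record with a complete pre-dose start date. Neither document says whether a new record is opened. The exposure is mainly in non-laboratory events and in laboratory findings already logged as AEs in screening.

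The frequency cannot be estimated from the documents. The effect per patient is at most 3.2, 5.6 or 7.7 points in cohorts of 31, 18 or 13.

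Two broader readings go too far. One is that every worsened screening event is absent from every TEAE table, or lost from the safety results altogether: this depends on how the record is kept, and Step 3 lists what is retained. The other is that dose-escalation decisions were affected because SAP 9.2 defines a DLT as treatment-emergent. The same condition could touch the DLT table, but Protocol 5.1 bases escalation on joint review of DLTs, treatment-related safety observations and other available data, not on that table.

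**What to change.** In SAP 9.3, define a TEAE as an AE with onset during the on-treatment period, or an AE with onset before the first dose that increases in CTCAE grade or becomes serious during that period. Report it at its worst on-treatment grade, and apply the definition to all tables in 9.3 a–e. State that the date of worsening is captured either by a new AE record or by a dated grade change. A new record is simpler, because Protocol 13.5.4 attaches severity, seriousness, action taken and causality to each record.

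The cost is one clause, the matching programming condition, and queries for screening AEs whose date of worsening was not captured. TEAE counts can only stay the same or rise, and may rise slightly. The change should be made before database lock; if that is no longer possible, it belongs in the clinical study report as a documented deviation, as SAP 1.2 provides.

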**12.3. Criteria for Evaluation****12.3.1. Safety**

All patients who receive at least dose of TTI-621 will be included in the safety analyses.

Adverse events, ECGs, LVEF assessments and laboratory data will be summarized and reviewed on an ongoing basis during the study. All adverse events, ECGs, LVEF assessments and safety laboratory abnormalities of potential clinical concern will be described. Safety data will be presented in tabular and/or graphical format and summarized descriptively by dose cohort and time where appropriate. Absolute value data and changes from baseline data will be summarized as appropriate.

AEs will be coded using the Medical Dictionary for Regulatory Activities (MedDRA) and severity of AEs and laboratory abnormalities will be graded using NCI CTCAE v5 as appropriate. Incidence tables of patients with AEs will be presented for all AEs by maximum severity, SAEs, AEs assessed as related to study drug and adverse events resulting in discontinuation of study drug.

For ECG analyses, the mean of the triplicate ECG parameters will be used as the observation for a patient at a nominal time point. Changes in ECG and laboratory measurements will be summarized.

Listings of all safety data sorted by dose cohort, patient and assessment date will be provided.

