### **13.3. Assessment of Causality**

The relationship of each adverse event to administration of the study drug(s) will be assessed by the Investigator after careful consideration of all relevant factors such as (but not limited to) the underlying study indication, co-existing disease, concomitant medication, relevant history, pattern of the adverse event, temporal relationship to receipt of the study medication(s) and de-challenge or re-challenge.

Study drug or study treatment refers to intravenously-administered doxorubicin and intravenously-administered TTI-621. The assessment of relationship to study drug or study treatment will be done for

each drug separately. If the Investigator feels such a distinction cannot be made, the assessment will be based on the combination of the two drugs.

The assessment of causality is based on the question of whether there was a reasonable causal relationship to the study drug in question according to the following guidelines:

**RELATED** (possible, probably or definitely related): there is a reasonable possibility that the study treatment caused the event; one or more of the following criteria apply:

- The event follows a reasonable temporal sequence from administration of study treatment
- The event could not be reasonably attributed to the known characteristics of the patient's clinical state, environment or toxic factors or other modes of therapy administered to the patient
- The event follows a known pattern of response to study treatment
- The event disappears or decreases on cessation or reduction in dose of the study treatment. In some situations, an AE will not disappear or decrease in intensity upon discontinuation of the study treatment despite other clear indications of relatedness

**UNRELATED** (unlikely related or definitely not related): There is no reasonable possibility that the study treatment caused the event; one or more of the following criteria apply:

- The event does not follow a reasonable temporal sequence from administration of study treatment
- The event could be reasonably attributed to known characteristics of the patient's clinical state, concurrent illness, environment or toxic factor or other therapies administered to the patient
- The event does not follow a known pattern of response to study treatment

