## 6.8 Data Display Characteristics

Data displays produced for this study will include three types—summary tables, data listings, and figures. Unless stated otherwise, data listings will be produced for all recorded data. Additional data listings will be produced for outcome measures that involve extensive procedures to derive the analyzed outcomes. Summary tables and figures will be produced when specified in sections to follow. All analyses will be performed using SAS (Statistical Analysis Software).

Data listings will simply list the data recorded on the CRF or derived for each subject. As needed, they can be ordered by dose cohort, site, subject number, and time of assessment, and additional levels of ordering hierarchy may reflect subsets of assessments within subject. Subject-level identifiers appear on the first line of data, and identifiers for subgroups within subject appear only on the first line of each subgroup value.

Tables will display summary statistics calculated for each dose cohorts per study phase (escalation/expansion), unless described otherwise in the following sections. For most summary tables, the dose group will be presented in column and the summary statistics of interest will be presented in rows. About tables labelling, the text “Number (%) of Subjects” will be incorporated in the title, either the primary title or as a separate subtitle, and no further labeling (e.g., “n (% )”) will appear in the body of the table.

The summary statistics displayed will be a function of the type of data associated with the summarized assessment. Unless stated otherwise in relevant sections to follow, continuous data will be summarized with the number of non-missing values, mean, standard deviation, minimum, median, and maximum. Categorical data will be summarized with the number of non-missing values and the numbers of values equal to each of the possible values. Percentages of subjects with each of the possible values will be calculated from the number of subjects in the corresponding analysis population, unless stated otherwise, and those percentages will be presented with one decimal (XX.X%). Some continuous variables may also be grouped into categorical levels and evaluated in frequency tables.

Pfizer Inc. / Protocol: TTI-621-03/C4961003  
IQVIA Biotech (Confidential) Project # YXA42460

Dates in the clinical database are classified into the categories of procedure dates, log dates, milestone dates, outcome dates, and special dates:

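### Causality is recorded for each drug, but none of the 12 treatment-related AE outputs in SAP 9.3 is split by the drug judged causal

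*SAP*

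**What the plan says.** Protocol 13.3 has the investigator assess relationship for "each drug separately. If the Investigator feels such a distinction cannot be made", the assessment rests on the two drugs together. SAP 9.3 agrees on what is collected: "The causality of AE are reported as either related to study drug or not related to study drug for each study drug".

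The next sentence of SAP 9.3 sets what is tabulated: "Related AEs are those related to any study drug (i.e., at least one of the study drugs". The outputs then follow under that definition, for example "Treatment-related TEAEs (separately for combination period and monotherapy period, and overall" and "Treatment related TEAEs leading to permanent discontinuation of PF-07901800".

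Protocol 12.3.1 promises incidence tables for "AEs assessed as related to study drug", and 13.3 defines study drug as both agents. On listings, SAP 6.8 says "Unless stated otherwise, data listings will be produced for all recorded data", and SAP 9.3 includes an all-AE listing among those introduced by "The following AE listings will be produced, sorted by dose cohort, patient, and timing, with relevant information".

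Causal relationship of adverse events is named in both safety endpoints: the primary one for escalation (SAP 3.1) and the secondary one for expansion (SAP 3.2).

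**The concern.** PF-07901800 is the drug under test. Doxorubicin is a fixed backbone with substantial toxicity of its own. The investigator makes a per-drug judgement for each event, and the planned tables then merge the two answers. A Grade 3 neutropenia blamed only on doxorubicin and a Grade 3 thrombocytopenia blamed only on PF-07901800 count alike as treatment-related.

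At stake is whether a reader of the study report can see, from a summary table, how much combination-period toxicity investigators put down to PF-07901800. The question is live. SAP 4.3.2 records that enrolment into Cohort B stopped after 18 patients because of Grade 3 or 4 thrombocytopenia at 2 mg/kg during combination therapy, and that 13 patients went into a new Cohort C at 1 mg/kg.

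**Working it through.** The plan states no figure to reproduce. The check is a count of the outputs titled treatment-related in SAP 9.3, by bulleted line, followed by a look at every other output that might fill the gap.

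**Count**

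| SAP 9.3 list | Treatment-related outputs | Split by period | Split by drug stopped | Neither | Split by drug judged causal |
|---|---|---|---|---|---|
| a, overall summary | 7 | 2 | 3 | 2 | 0 |
| b, by SOC and PT | 4 | 1 | 1 | 2 | 0 |
| c, by PT | 1 | 0 | 0 | 1 | 0 |
| Total | 12 | 3 | 4 | 5 | 0 |

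- The 3 split by period are related TEAEs and related Grade 3 or higher TEAEs in list a, and related TEAEs in list b.
- The 4 split by drug stopped are the related discontinuation lines.
- The remaining 5 (12 − 3 − 4) are related serious TEAEs and related deaths in lists a and b, and the most common related TEAEs in list c.

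**Possible substitutes**

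- *DLT summary.* SAP 9.2 requires a DLT to be related to PF-07901800 or to the combination, so this output does tie events to the test drug. It covers Cycle 1 only, and SAP 6.7.3 limits its analysis set to the escalation cohorts. The expansion cohorts, about 62 patients (31 in A, 18 in B, 13 in C), are outside it.
- *Monotherapy-period rows.* These largely isolate PF-07901800, but they start only once the combination period has ended, 21 days after the last doxorubicin dose. They do not describe the combination.
- *Discontinuation rows.* These name the drug stopped. Under the pooled definition, an event blamed only on doxorubicin that led to stopping PF-07901800 still counts as related. Protocol 5.3 makes this possible: an unacceptable event clearly put down to doxorubicin before four cycles have been given ends all study treatment.
- *Dose-reduction and interruption tables.* These are also split by drug, by SOC and PT as well as overall, and they cover Cohorts A to C. They carry some attribution, because protocol Tables 13 and 14 act on TTI-621 for TTI-621-associated events and Table 18 acts on doxorubicin. The link is broken in several places. The platelet rules (Table 22; see the note to Table 13) apply whichever drug is blamed. Table 21 reduces both drugs when attribution is not possible. Protocol 5.2 holds TTI-621 whenever doxorubicin is held for a recoverable event.
- *Special-interest and infusion-reaction summaries (lists d and e).* These carry no relatedness at all.
- *All-AE listing.* Per-drug causality should appear here under SAP 6.8, but a reader would have to count it patient by patient.

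So outside the Cycle 1 DLT summary, no combination-period summary gives related TEAEs, related Grade 3 or higher TEAEs, related serious TEAEs or related deaths by attribution to PF-07901800.

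**The case against.** The strongest reply is that the SAP delivers what the protocol promised. Study drug means both agents in protocol 13.3, and 12.3.1 asks only for events related to study drug. Per-drug attribution is also weak evidence here: the study is open-label, both drugs are on board, and the synopsis concedes that assigning cause to one agent may be difficult. If inseparable events are counted under each drug, overlapping cytopenias will appear in both columns, and the PF-07901800 column may come close to the pooled one. Better evidence on PF-07901800 comes from all-cause, special-interest and laboratory shift tables across dose cohorts on a fixed doxorubicin dose, and these are planned. The reduction and interruption tables add a partial view by drug.

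Most of this stands. It shows that the added columns should not replace anything. It does not show that they are useless. Causal relationship is part of both safety endpoints, the judgement is already collected, and several management rules depend on it. The cohort comparison can show a gradient between PF-07901800 doses, but with no doxorubicin-only cohort it does not show the excess over doxorubicin. The tables split by drug acted on are a proxy only, for the reasons given in the working.

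**Conclusion.** The point holds as a worthwhile, low-cost improvement to the planned tables. Its size is structural: 0 of 12 treatment-related outputs are split by the drug judged causal, and the only combination-period summary tied to PF-07901800 attribution is the Cycle 1 DLT summary in escalation. The conclusion assumes that per-drug causality is on the AE eCRF as SAP 9.3 describes and that the all-AE listing will show it.

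A reader might infer more than the documents support:

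- *That the SAP contradicts the protocol.* It does not; 12.3.1 does not ask for per-drug tables.
- *That attribution to PF-07901800 goes unreported.* It should be in the AE listing; what is missing is the summary.
- *That dose selection or a decision rule is compromised.* No decision rule uses these tables, and the cohort tables can still show a dose gradient.
- *That the pooled rates are mostly doxorubicin toxicity.* The documents give no doxorubicin-related event rate, so the doxorubicin-only share of any pooled row is unknown. Single terms that doxorubicin rarely causes would be little affected.
- *That any doxorubicin toxicity before four cycles ends all treatment and so inflates the PF-07901800 discontinuation row.* Protocol 5.3 covers only unacceptable events, and Table 18 handles many others by dose reduction. The SAP also leaves open whether the PF-07901800, doxorubicin and both-drug rows overlap. That is missing table detail rather than an error.

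**What to change.** In SAP 9.3, keep the any-drug tables as they are. Beside them add PF-07901800-related and doxorubicin-related counts, by cohort, for the combination period and overall, for:

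- related TEAEs, any grade and Grade 3 or higher, by SOC and PT;
- related serious TEAEs;
- related TEAEs leading to death or to discontinuation;
- the adverse events of special interest.

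Count an event related to both drugs, or not separable under protocol 13.3, under each drug, and say so in a footnote.

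The cost is extra columns built from variables already collected; no new data are needed. The drawback is that open-label attribution by drug is subjective and the two columns will overlap and not sum to the pooled count. They should therefore be labelled as supplementary to the pooled and all-cause tables.
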